
To evaluate the effect of atogepant 60 mg QD versus placebo on Physical Impairment
	
CFB in mean monthly Physical Impairment domain score of the AIM-D across the 12-week treatment period

For the European Union only:
 
To evaluate the effect of atogepant 60 mg QD versus placebo on the impact of headaches on daily functioning as assessed by Headache Impact Test (HIT-6)
	
For the European Union only:
 
CFB in the HIT-6 total score at Week 12

Overall Study Design:

- This is a global, multicenter, randomized, double-blind, placebo-controlled, parallel group study in participants with episodic migraine who have previously failed 2 to 4 classes of oral medications for the prophylaxis of migraine

Key Inclusion Criteria

Selected key inclusion criteria are presented below:

Age
Male or female participants ages 18 (or age of legal majority) to 80 years, inclusive, at Visit 1
Type of Participant and Migraine Characteristics
At least a 1-year history of migraine with or without aura consistent with a diagnosis according to the ICHD-3, 2018 .
Age of the participant at the time of migraine onset < 50 years
History of 4 to 14 migraine days per month on average in the 3 months prior to Visit 1 in the investigator's judgment
4 to 14 migraine days in the 28-day baseline period per eDiary (Note: A randomization cap of 20% will be instituted to ensure that the planned randomized participants include no more than 20% of participants with 4 to <8 migraine days at baseline.)
Completed at least 20 out of 28 days in the eDiary during the baseline period and is able to read, understand, and complete the study questionnaires and eDiary per investigator's judgment.

Participants must meet both criteria below (ie, a and b). Participants must have

- a. Failed oral migraine prophylaxis medications from 2 to 4 of the medication classes as listed below:
 - i. Propranolol, metoprolol, atenolol, bisoprolol, timolol, or nadolol;
 - ii. Topiramate;
 - iii. Flunarizine;
 - iv. Valproate or divalproex;
 - v. Amitriptyline or nortriptyline;
 - vi. Venlafaxine or desvenlafaxine;
 - vii. Lisinopril;
 - viii. Candesartan;
 - ix. Locally approved products (eg, oxeterone or pizotifen)
- b. Failed at least one treatment from the list below:
 - i. Propranolol OR metoprolol;
 - ii. Topiramate;
 - iii. Flunarizine;
 - iv. Amitriptyline;

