- 3) The dropout rate is assumed to be 15% for endpoints other than AIM-D related endpoints. The dropout rate for AIM-D endpoints is 21%. A higher missing rate for AIM-D endpoints was observed in the Advance Study because the related measure was collected only in Today's eDiary instead of both Yesterday and Today's eDiary, If the participants may provide less than 14 records of Today's eDiary within a 28-day period, it would lead to missing data.

The assumptions of sample size calculation such as SD and dropout rate will be monitored while the study is ongoing and sample size will be adjusted. This blinded analysis of variability in the pooled treatment groups will be performed using the primary efficacy analysis model for the primary endpoint as described in Section 9.4.1.2 but excluding the terms treatment and treatment by visit interaction from model terms.

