9.4.1.1.4. Collection and Derivation of Primary and Secondary Efficacy Assessments

On a daily basis during the 28-day baseline period and throughout the study, participants are to record into an eDiary information on the daily total duration of headache, headache specific characteristics and symptoms, the worst pain severity, and use of any acute headache pain medication. Participants will be able to report headache data, including absence of headache, for the day of the eDiary report and for the day immediately prior to the day of the eDiary report, as long as information reported is for a time subsequent to the participant's most recent report. This is defined as a one-day "missing-recall" window.

Following randomization on Day 1, there are 4 visits at 2-week intervals, followed by 2 visits at 4-week intervals; altogether encompassing a 12-week double-blind treatment phase of the study and a 4-week safety follow-up phase. In practice, there may or may not be exact 2-week or 4-week durations between two consecutive visits and the visits might not align with each 28-day period recorded in the eDiary (ie, Weeks 1 to 4, 5 to 8 and 9 to 12, corresponding to Days 1 to 28, 29 to 56, and 57 to 84). Therefore, for data analysis purposes, the number of migraine days during the last 28 days prior to the randomization date, will serve as the "baseline", and change from baseline will be calculated for consecutive 28-day periods beginning with the date of the first dose of study intervention.

In order to be randomized, a participant should be in the screening/baseline period for at least 28 days and must report eDiary data for at least 20 days (including missing recall) during the 28-day screening/baseline period. If less than 28 days of baseline data are reported, the number of headache days and other such counting variables for “baseline” will be prorated to standardize the count to a 28-day equivalent. Subsequent to treatment start, the number of headache days will be counted in successive and non-overlapping 4-week (ie, 28-day) windows. Headaches that continue into a subsequent 4-week period will be counted (with recorded severity and duration) as occurring in each period.

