The secondary endpoints for headache days, acute medication use days, Performance of Daily Activities domain score of the AIM-D, and Physical Impairment domain score of the AIM-D will be analyzed in the same manner as that used to analyze the primary endpoint. For MSQ v2.1 Role Function Restrictive domain score and HIT-6 total score, the analysis will be performed similarly to the primary MMRM, with focus on the pairwise contrasts of atogepant dose group to placebo at Week 12. Some participants may have MSQ v2.1 or HIT-6 assessed at Visit 8, which will not be included in MMRM

models. Note that the stratification of number of migraine days during the screening/baseline period (4 to  $< 8$  and  $\geq 8$ ) will be included in the secondary efficacy analyses if baseline values other than monthly migraine days are included in the corresponding models.

The 50% responder, defined as a participant with the achievement of at least a 50% reduction from baseline in the 3-month average of monthly migraine days, will be assessed for each participant. A logistic regression model will be used to analyze the 50% responders across the 12-week treatment period. This model assumes a binary distribution for the response and uses a logit link. The analysis model will include treatment group, region, the stratification of number of classes of failed prior prophylactic treatments (2 and  $>2$ ), and baseline monthly migraine days. The treatment difference in terms of odds ratio between each atogepant dose group and placebo will be estimated and tested from this model.

For the analyses in the mITT population, the 50% responder will be derived using data collected from the double-blind period. For the analyses in Off-treatment Hypothetical Estimand population, the 50% responder will be derived using data collected from the double-blind period and follow-up period; data after participants started a new prophylaxis treatment during the follow-up period will be excluded.

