## **Appendix B. Derivation of Efficacy Variables**

### **A.1 Derivation of Efficacy Endpoints Based on eDiary Data**

For analysis purposes, four weeks (28 days) will be considered as one month. On a daily basis during the 4-week baseline period and throughout the double-blind treatment period, participants are to record eDiary information on the duration of headache, headache specific characteristics and symptoms, the pain severity, and use of any acute headache pain medication (see protocol Sections 8.1.1, 8.1.2, 8.1.3). Daily headache diary data consists of data from "today's diary" completed on that day and "yesterday's diary" completed on the following day. Participants are to report headache data in "today's diary" in the evening at any time from 19:00 to 23:59 and to complete "yesterday's diary" on the following day to add the remaining headache data of previous evening until midnight. In case participants miss "today's diary," they can report the whole-day headache data in "yesterday's diary" on the following day. In case participants miss "yesterday's diary," headache data from "today's diary" alone will be used as daily headache diary data. If both "today's diary" and "yesterday's diary" are missing on one day, the daily headache diary data will be treated as missing.

Daily headache diary data will be merged from "today's diary" and "yesterday's diary" as following and will be used to derive migraine day and headache day.

- Daily headache total duration: summation of headache durations from "today's diary" and "yesterday's diary"
- Daily headache pain severity: the worst pain severity from "today's diary" and "yesterday's diary"
- Daily headache characteristics and symptoms: present if present in one of "today's diary" and "yesterday's diary"
- Daily acute headache medication usage: combination of acute headache medications usage from "today's diary" and "yesterday's diary."
- For the derivation of headache day, the participant is considered to have taken a non-antiemetic acute headache medication if the participant has taken such a medication in either "today's diary" or "yesterday's diary."

Moderate/severe headache day is defined as a headache day during which the maximum pain severity is either moderate or severe. Severe headache day is defined as a headache day during which the maximum pain severity is severe.

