## A.2 Derivation of Health Outcome Endpoints

### AIM-D Related Endpoints Derivation

The AIM-D was developed as a daily eDiary with a recall period 24 hours. By design, it is collected in the today diary only. The scoring of the following endpoints is completed in 2 steps.

- Monthly Performance of Daily Activities domain score of the AIM-D
- Monthly Physical Impairment domain score of the AIM -D
- Monthly AIM -D total score

Step 1: Calculate AIM-D daily domain score and total score

Daily performance of daily activities score will be calculated based on the summation of items 1-5 and 10 and 11, ranging from 0-35. A daily performance of daily activities domain score will be calculated if 4 or more item scores have non-missing responses. When the response category "I did not have <errands, leisure or social, strenuous activities> planned" (items 2, 4, and 5), is selected, the response will be considered missing. The corresponding performance of daily activities domain score will be calculated by summing the non-missing item scores and dividing by the number of non-missing items and then multiplying by 7, provided that 4 or more item scores are available; otherwise, it will be set to missing. The raw daily score will be transformed to a 0-100 scale by multiplying by 100 and dividing by the highest raw score (35).

Daily physical impairment scores will be calculated based on the summation of items 6-9, ranging from 0-20. A daily physical Impairment score will be calculated if 2 or more item scores have non-missing responses. The corresponding physical Impairment score will be calculated by summing the non-missing item scores and dividing by the number of non-missing items and then multiplying by 4, provided that 2 or more item scores are available; otherwise, it will be set to missing. The raw daily score will be transformed to a 0-100 scale by multiplying by 100 and dividing by the highest raw score (20).

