#### Step 2: Calculate Monthly Scores and Baseline Score

Monthly scores will be calculated using the average daily scores only if there are at least 14 non-missing daily scores in the corresponding monthly (28-day) period. The corresponding monthly scores will be calculated by summing the non-missing daily domain scores and dividing by the number of non-missing daily domain, provided that 14 or more daily scores are available; otherwise, it will be set to missing.

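### The 20-day baseline diary rule does not secure an AIM-D baseline, so the US S5 and S6 models can drop randomised mITT participants whom the estimands include

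*Protocol*

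**What the plan says.** **Entry.** Inclusion criterion 2.05 (Protocol 1.1 and 5.1) asks that the participant has "Completed at least 20 out of 28 days in the eDiary during the baseline period". Protocol 9.4.1.1.4 explains the count: the participant "must report eDiary data for at least 20 days (including missing recall) during the 28-day screening/baseline period". SAP Appendix B, A.1 confirms that a day with no same-day entry is still valid, because participants who miss it "they can report the whole-day headache data in" the next day's diary.

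**AIM-D scoring.** SAP Appendix B, A.2 says of AIM-D: "By design, it is collected in the today diary only". Step 2 of that derivation, whose heading covers both the monthly and the baseline scores, adds: "Monthly scores will be calculated using the average daily scores only if there are at least 14 non-missing daily scores". Below that number the score is missing.

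**Population and model.** SAP Table 5 names mITT as the population for US S5 and S6. By SAP section 4.0, mITT needs an evaluable eDiary baseline. The only day count given for one is 20 days, for migraine days and the diary counts derived the same way (Appendix B, A.1). Nothing requires an AIM-D baseline. SAP 9.4.2 states that the "Physical Impairment domain score of the AIM-D will be analyzed in the same manner as that used to analyze the primary endpoint", and it treats the Performance of Daily Activities score likewise. The primary model (Protocol 9.4.1.2, SAP 9.3.2) is an MMRM of change from baseline, with baseline and baseline-by-visit as covariates, on observed cases without imputation.

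**Allowance for loss.** Protocol 9.2 assumes 21% loss for AIM-D endpoints against 15% for the others, and gives the reason: "A higher missing rate for AIM-D endpoints was observed in the Advance Study because the related measure was collected only in Today's eDiary".

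**The concern.** The migraine-day baseline is secured: 20 days are needed to enter and 20 to be analysed. The AIM-D baseline is not, because the two instruments count different days.

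The consequence is larger than for a gap during treatment. A missing treatment month costs one of three visits. A missing baseline removes both the response and the covariate, so all three visits go, however well the participant completed the diary later. No text says how to handle a missing AIM-D baseline.

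Two things are at stake. The analysed set for S5 and S6 becomes a subset of mITT, selected on diary habits, while the estimand names mITT. And precision is lost on the last two tests in the US sequence, including S6, which has the lowest stated power (81%).

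**Working it through.** **1. Can the entry rule be met without an AIM-D baseline?** Yes. With exactly 20 reported days, 13 same-day and 7 recalled, the rule is met (13 + 7 = 20) but 13 < 14, so the AIM-D baseline is missing. With all 28 days reported, 13 same-day and 15 recalled gives the same result.

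**2. Reproducing the plan's power.** Inputs from Protocol 9.2 and Table 9-1: 150 per arm, two-sided alpha 0.05, AIM-D loss 21%; S5 difference 3.3, SD 7.3; S6 difference 2.4, SD 6.4. Two-sample t power uses noncentrality δ / (σ√(2/n)) with 2n − 2 degrees of freedom, and n = 150 × 0.79 = 118.5.

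- S6: 2.4 / (6.4 × 0.1299) = 2.887, power 82.0% (stated 81%).
- S5: 3.3 / (7.3 × 0.1299) = 3.480, power 93.4% (stated 93%).

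The stated figures reproduce.

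**3. Most that recovery could add.** The AIM-D excess is 21 − 15 = 6 points, or 18 of 300 participants. If some of it is baseline loss and is fully recovered:

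| Points recovered | n per arm | S5 power | S6 power |
|---|---|---|---|
| 0 | 118.5 | 93.4% | 82.0% |
| 2 | 121.5 | 93.9% | 82.9% |
| 4 | 124.5 | 94.4% | 83.8% |
| 6 | 127.5 | 94.9% | 84.7% |

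The ceiling is 84.7 − 82.0 = 2.7 points for S6 and 94.9 − 93.4 = 1.5 for S5.

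**4. If baseline loss comes on top of the 21%.** Assume it takes 2%, 5% or 10% of the remaining participants:

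| Extra loss | n per arm | S5 power | S6 power |
|---|---|---|---|
| 2% | 116.1 | 92.9% | 81.2% |
| 5% | 112.6 | 92.2% | 80.0% |
| 10% | 106.7 | 90.8% | 77.8% |

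S6 reaches 80% at a total AIM-D loss of about 25%.

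**5. How often might it happen?** The documents give no same-day completion rate, so everything here is assumed.

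- Identical participants, independent days. For daily same-day / recall-only probabilities of 0.80/0.10, 0.70/0.15, 0.60/0.20 and 0.50/0.30, the share of those passing the 20-day rule with fewer than 14 same-day entries is 0.01%, 0.5%, 7.0% and 38.5%.
- Participants who differ. Let the same-day probability follow a beta distribution with mean 0.70 to 0.85, and let a missed day be caught up with probability 0.5 or 0.7. With beta concentration 5 or more, the share runs from near 0% to 14.9%. At mean 0.75 and catch-up 0.7 it is 10.0%, 5.5%, 2.5% and 0.8% for concentrations 5, 10, 20 and 50. A wider spread (concentration 3) takes the worst corner, mean 0.70 and catch-up 0.7, to 18.3%.

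The between-person spread drives the answer, and nothing in the documents fixes it.

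**6. How much does each recovered participant bring?** Poor same-day reporters at baseline tend to stay poor. At mean 0.75, catch-up 0.7 and concentration 5 to 10, only 16% to 29% of those without a baseline have all three treatment months evaluable, and 22% to 42% have none. Step 3 counts each recovered participant as complete, so it overstates the gain.

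**7. Does the repair work?** In 4,000 simulated ANCOVA trials with a true difference of −2.4, filling a missing baseline with the pooled mean gave average estimates of −2.38 to −2.40. Power rose from 81.8% to 82.9% with 6% of participants recovered (+1.1 points) and from 80.8% to 83.1% with 10% recovered (+2.3 points).

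**The case against.** The plan is not blind to this. It names same-day collection as the cause of extra AIM-D loss and budgets 21% for it. If that figure already includes baseline loss, the stated powers stand as they are. Criterion 2.05 also asks for the investigator's judgement that the participant can complete the diary, the schedule lists AIM-D in the Visit 2 diary review, and Protocol 10.8.2 makes that review part of eligibility. S6 is last in the sequence, so its failure blocks nothing. The 14-score rule reaches baseline only through the Step 2 heading, and exclusion for a missing baseline is inferred from the model.

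Most of this stands as a limit on size. It does not close the gap: the Visit 2 review sets no minimum number of AIM-D entries, and a model of change from baseline on observed cases cannot use a participant without a baseline. If the 20-day minimum were applied to AIM-D instead of 14, the gap would be wider.

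A reader might infer three stronger things that the documents do not support:

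- **The treatment comparison is biased.** The loss is fixed before treatment starts, so it cannot depend on the arm.
- **Most AIM-D missingness arises at baseline.** In the plan's own split, 15 of the 21 points apply to every endpoint. The AIM-D excess is at most 6/21 = 29% of the total and may fall in any period.
- **The entry criterion should be tightened.** That would screen-fail or delay otherwise eligible participants for a small gain. It is also too late: SAP 2.3 (version 2.0, August 2022) reports in the past tense that nobody was enrolled from Asia/Pacific, which implies that enrolment had ended.

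**Conclusion.** The concern holds in limited form. An mITT participant can lack an AIM-D baseline, and the S5 and S6 models as written then drop that participant entirely, so the analysed set is narrower than the population the US estimands name.

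The likely benefit of repair is about 1 to 2 points of S6 power, at most 2.7 if all 6 excess points were baseline loss and fully recovered, and less for S5. The frequency is unknown; near 0% to about 15% rests wholly on assumed diary compliance and on how much participants differ. The stated powers are not in error. Whether S6 could fall below 80% depends on whether the 21% includes baseline loss, which the documents do not say. The cost is in precision and in the match between estimand and analysis. The primary endpoint and S1 to S4 are untouched.

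**What to change.** In SAP 9.4.2, for US S5 and S6, keep every mITT participant who has at least one evaluable post-baseline AIM-D month, including those with no AIM-D baseline. Choose one method in advance:

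- set the missing baseline to the baseline mean pooled over both arms, and model the monthly score with baseline as a covariate; or
- fit a constrained longitudinal model in which baseline is one of the repeated measures, with a common mean in both arms.

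Say in the body of Appendix B Step 2 that the 14-score rule applies to baseline, and state in SAP 2.4 whether the 21% includes baseline loss. Report by arm how many mITT participants have no AIM-D baseline.

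The cost is a few sentences and some programming, with no extra participants and no change to entry criteria. Recovered participants will carry less information than complete ones, and those with no evaluable treatment month stay out.

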1.2. Schema

Figure 1-1 Study Diagram

1.3. Schedule of Activities (SoA)

PRO measures should be administered prior to any tests and/or evaluations with the exception of Visit 1 (Screening/Baseline) and Visit 2 (Randomization) because in those respective visits, the examinations and assessments required for the verification of inclusion/exclusion criteria are to be performed first.

Table 1-1 Schedule of Activities

Study Period	Screening/Baseline Period (4 weeks)	Double-blind Treatment Period (12 weeks)						Safety Follow-up Period (4 weeks)
		Visit 1 (Screening/Baseline)	Visit 2 (Randomization)	Visit 3	Visit 4	Visit 5	Visit 6	
Day/Week	Week -4	Day 1	Week 2 (Day 14)	Week 4 (Day 28)	Week 6 (Day 42)	Week 8 (Day 56)	Week 12 (Day 84)	Week 16 (Day 112)
Visit Windows	Day -35 to Day -28	NA	± 3 day	± 3 day	± 3 day	± 3 days	+ 3 days	± 3 days
Obtain informed consent	X							
Obtain informed consent for PK (optional)	X							
Randomization		X						
Obtain VCT consent and perform verification (United States only)	X							
Access IWRS	X	X	X	X	X	X	X	X
Assess inclusion/exclusion criteria	X	X						
Collect demographic information	X							
Collect medical history	X							
Collect migraine history	X							
Review prior medications including migraine prophylactic medication use and complete Treatment Failure Worksheet	X							
Perform physical examination	X						X	X
Collect vital sign measurements ^d	X	X	X	X	X	X	X	X
Perform ECG	X				X		X	

Study Period	Screening/Baseline Period (4 weeks)	Double-blind Treatment Period (12 weeks)						Safety Follow-up Period (4 weeks)
		Visit 1 (Screening/Baseline)	Visit 2 (Randomization)	Visit 3	Visit 4	Visit 5	Visit 6	
Day/Week	Week -4	Day 1	Week 2 (Day 14)	Week 4 (Day 28)	Week 6 (Day 42)	Week 8 (Day 56)	Week 12 (Day 84)	Week 16 (Day 112)
Visit Windows	Day -35 to Day -28	NA	± 3 day	± 3 day	± 3 day	± 3 days	+ 3 days	± 3 days
Perform pregnancy test ^e	X	X	X	X	X	X	X	X
Perform urine drug screen	X							
Clinical laboratory determinations ^f	X	X	X	X	X	X	X	X
PK sample collection (for those participating) ^g		X	X	X	X	X	X	
Provide eDiary, and eDiary instructions and training ^h	X							
Participant daily eDiary data collection	X	X	X	X	X	X	X	X ^s
Review of study intervention compliance			X	X	X	X	X	
Review eDiary data (eg, headache duration, frequency, characteristics, symptoms, acute medication use, AIM-D, activity level and activity limitation) and compliance ^{i,j}		X	X	X	X	X	X	X ^s
Healthcare Resource Utilization	X	X	X	X	X	X	X	
C-SSRS ^{k,l}	X	X	X	X	X	X	X	X
ASC-12 (eTablet) ^m	X							
HIT-6 (eTablet) ^m		X		X		X	X	X
PGIC (eTablet) ^m							X	
PGI-S (eTablet) ^m		X		X		X	X	
WPAI: MIGRAINE (eTablet) ^m		X		X		X	X	
PSSM (eTablet) ^m				X		X	X	
EQ-5D-5L (eDiary or eTablet) ^{m,n}	X	X	X	X	X	X	X	X
MIDAS (eTablet) ^m		X					X	
MSQ v2.1 (eTablet) ^m		X		X		X	X	X

Study Period	Screening/Baseline Period (4 weeks)	Double-blind Treatment Period (12 weeks)						Safety Follow-up Period (4 weeks)
		Visit 1 (Screening/Baseline)	Visit 2 (Randomization)	Visit 3	Visit 4	Visit 5	Visit 6	
Day/Week	Week -4	Day 1	Week 2 (Day 14)	Week 4 (Day 28)	Week 6 (Day 42)	Week 8 (Day 56)	Week 12 (Day 84)	Week 16 (Day 112)
Visit Windows	Day -35 to Day -28	NA	± 3 day	± 3 day	± 3 day	± 3 days	+ 3 days	± 3 days
PROMIS-PI (eTablet) ^m		X		X		X	X	
PHQ-9 (eTablet) ^m		X					X	
Dispense study intervention		X ^o	X	X	X	X		
Collect eDiary		X ^p					X ^q	X ^r
Adverse events	X	X	X	X	X	X	X	X
Concomitant medications/concurrent procedures	X	X	X	X	X	X	X	X

ASC-12 = 12-item Allodynia Symptom Checklist; AIM-D = Activity Impairment in Migraine–Diary; C-SSRS = Columbia Suicide Severity Rating Scale; ECG = electrocardiogram; eDiary = electronic diary; EQ-5D-5L = European Quality of Life – 5 Dimensional; ET = early termination; eTablet = electronic tablet; HIT-6 = Headache Impact Test; INR = international normalized ratio; IWRS = interactive web response system; MIDAS = Migraine Disability Assessment; MSQ v2.1 = Migraine Specific Quality of Life Questionnaire, Version 2.1; PGIC = Patient Global Impression of Change; PGI-S = Patient Global Impression – Severity; PHQ-9 = Patient Health Questionnaire; PK = pharmacokinetic; PRO = patient-reported outcome; PSSM= Patient Satisfaction with Study Medication, PROMIS-PI = Patient-Reported Outcomes Measurement Information System Pain Interference – Short Form 6a; VCT = verified clinical trial; WPAI:MIGRAINE = Work Productivity and Activity Impairment Questionnaire: Migraine V2.0.

- ^a Visit 1 and Visit 2 must be conducted in the office. All other visits, should be conducted in the office unless it is necessary to conduct remote visits for the safety of participants or study personnel (eg, COVID-19 or other pandemic situation): for details please refer to the Schedule of Activities for Remote Visits in Section 10.11 (Appendix 11).
- ^b Effort should be made by site to not schedule Visit 7 earlier than 12 weeks after Day 1 (Day 84) to ensure that participants complete the full 12 weeks of treatment and have eDiary data through Day 84.
- ^c All participants who take at least 1 dose of study intervention must complete the safety follow-up period, except participants rolling over into Study 3101-312-002 (long-term safety extension study). For these rollover participants the Follow-up Visit will be performed at the end of the long-term safety extension study
- ^d Vital sign measurements: height, weight, sitting and standing pulse rate, respiratory rate, sitting and standing systolic and diastolic blood pressure, and body temperature. Height will be measured only at Visit 1.
- ^e For females of childbearing potential only, urine pregnancy tests will be performed.
- ^f Clinical laboratory determinations include chemistry, hematology, coagulation parameters (INR), and urinalysis to be collected for all study visits. Samples for serology and the urine drug screen will be collected only at screening (Visit 1).
- ^g PK sample should be collected prior to the first dose at Visit 2, 1 sample should be collected prior to the daily dose taken during one of the Visits 3 to 6, and the remaining samples should be collected 1 to 10 hours post the daily dose.
- ^h Participant should begin using the eDiary as soon as it is dispensed. If it is subsequently determined that the participant has failed entry criteria, the eDiary should be returned to site.
- ⁱ Participants should bring eDiary to visits and review with coordinators.
- ^j Data to be captured in the eDiary on a daily basis
- ^k At Visit 1, the *Screening/Baseline* assessment of the C-SSRS will be completed. At all other study visits, the *Since the Last Visit* C-SSRS will be completed.
- ^l Clinicians will complete the C-SSRS on eTablet.
- ^m PRO measures should be administered prior to any tests and/or evaluations unless indicated otherwise in the protocol (eg, during randomization visit, some tests will be conducted prior to PROs for eligibility).
- ⁿ EQ-5D-5L will be collected via an eDiary for a period of 1 week in the screening period (administered between the 22nd and 28th days of the Screening/baseline period for a total of 7 days), randomization (Study Day 1) until Visit 3 (14 consecutive days from randomization), Visit 4 (\pm 3 days ie, Study Days 25 to 31 from randomization for a total of 7 days), Visit 5 (\pm 3 days ie, Study Days 39 to 45 from randomization for a total of 7 days), Visit 6 (\pm 3 days ie, Study Days 53 to 59 from randomization for a total of 7 days), and Visit 7 ($-$ 7 days ie, Study Days 77 to 83 from randomization for a total of 7 days). At Visit 8, the EQ-5D-5L will be administered in an eTablet.
- ^o The first dose of study intervention should be taken at the study site
- ^p Collected at Visit 2 only for participants who fail screening
- ^q Collected at Visit 7/ET only for participants who complete the double-blind treatment period
- ^r Collected at Visit 8/EOS only for participants who terminate early from the double-blind treatment period
- ^s For participants who terminate early from the double-blind treatment period only.

2. Introduction

Atogepant is a potent, selective oral calcitonin gene-related peptide receptor antagonist (CGRP-RA) being developed for the prophylaxis of migraine.

